5 ABORTIONS

Any spontaneous abortion in a participant exposed to study treatment or the partner of a male participant exposed to study treatment should be classified as an SAE (as the Sponsor considers spontaneous abortions to be medically significant events), recorded on the Adverse Event eCRF, and reported to the Sponsor immediately (i.e., no more than 24 hours after learning of the event; see Section 5 of [Appendix 2](#)).

Any induced abortion due to maternal toxicity and/or embryofetal toxicity should also be classified as an SAE, recorded on the Adverse Event eCRF, and reported to the Sponsor immediately (i.e., no more than 24 hours after learning of the event; see Section 5 of [Appendix 2](#)).

Elective or therapeutic abortion not associated with an underlying maternal or embryofetal toxicity (e.g., induced abortion for personal reasons) does not require expedited reporting and is not considered an AE but should be reported as outcome of pregnancy on the Clinical Trial Pregnancy Reporting Form.

All abortions should be reported as pregnancy outcomes on the paper Clinical Trial Pregnancy Reporting Form.

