4.1.1.3 Stopping Rules Criteria

4.1.1.3.1 Cohort Stopping Rules

Part 1

Dose escalation will be stopped and dosing at a given level will be stopped if one of the following circumstances occurs in participants treated with RO7565020 within the same dose cohort:

- Severe non-serious adverse reactions (Grade 3 or above, as per Division of AIDS [DAIDS] grading, v2.1, considered to be related to RO7565020) in 2 or more participants receiving RO7565020 in the same cohort, independent of the system organ classes.
- Any serious adverse reaction in 1 participant (i.e., a serious AE [SAE] considered to be related to RO7565020).
- Grade 2 or above clinically significant laboratory abnormalities, vital sign change, or ECG change, of the same type in 3 or more participants receiving RO7565020 in the same cohort.
- Other findings, which at the discretion of the DDT, indicate that dose escalation or dosing at that dose level should be stopped.
- Dose escalation will also be stopped if increasing the dose does not result in a significant increase in serum exposure of RO7565020.

Parts 2 and 3

Dose escalation and dosing at a given level of RO7565020 will be temporarily halted if one of the following circumstances occurs. Dosing might be resumed if deemed appropriate following the DDT review of the available safety, PK, and PD data. Relevant reporting and discussion with relevant DDT personnel and the Institutional Review Board (IRB)/ Independent Ethics Committee (IEC) will take place before potential resumption of dosing.

- Severe non-serious adverse reactions (Grade 3 or above, as per DAIDS grading, v2.1, considered to be related to RO7565020) in 2 or more participants receiving RO7565020 in the same cohort, independent of the system organ classes
- Any serious adverse reaction in 1 participant (an SAE considered to be related to RO7565020)
- Other findings which, at the discretion of the DDT members, indicate that dose escalation or dosing at that level should be stopped

In case dose escalation is stopped, lower doses within the tolerated dose range could be investigated or a dose repeated in subsequent cohorts to increase the amount of data within this tolerated dose range.

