9.4.2 Safety Analyses

All safety analyses will be based on the safety analysis set (see [Table 11](#)). Participants will be summarized by cohort. In addition, all study participants who are randomized to receive SC or IV placebo will be pooled as respective SC or IV placebo control groups, according to each part of the study.

The safety data, including AEs, injection-site reactions, reasons for withdrawal from study, laboratory data, ECG, concomitant medications, vital signs, and physical examination results will be listed and summarized descriptively. Marked abnormalities of laboratory data will be flagged. As appropriate, listings, summary tables and graphs (participant plot and/or mean plots) will be provided to describe safety and tolerability assessments.

Table 11 Safety Statistical Analysis Methods

| Endpoint | Statistical Analysis Methods |
|---------------------------|--|
| Adverse events | The original terms recorded on the eCRF by the Investigator for AEs will be coded by the Sponsor. AEs will be summarized by mapped term and appropriate thesaurus level. Frequency and severity of adverse events will be summarized. |
| Clinical laboratory tests | All clinical laboratory data will be stored on the database in the units in which they were reported. Laboratory test values will be presented in International System of Units (SI units) by individual outputs with flagging of abnormal results. Summary tables of absolute value and change from baseline over time will be displayed. Shifts in DAIDS grades v2.1 from baseline to the worst grade observed during treatment will be presented for selected laboratory parameters. For details on standard reference ranges and data transformation and the definition of laboratory abnormalities, see Appendix 4 . |
| Vital signs | Vital sign data will be presented with flagging of values outside the normal ranges and flagging of abnormalities. Mean changes from baseline and absolute value over time will be provided. |
| ECG data analysis | ECG data will be presented using appropriate outputs, as detailed in Section 9.4.2.1 . |
| Concomitant medications | The original terms recorded on the participants' eCRF by the Investigator for concomitant medications will be standardized by the Sponsor by utilizing a mapped term and appropriate drug dictionary level. Concomitant medications will be presented using appropriate outputs. |

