1. DEFINITION OF ADVERSE EVENTS

According to the E2A International Council for Harmonisation (ICH) guideline for Good Clinical Practice (GCP), an **adverse event** (AE) is any untoward medical occurrence in a participant or clinical investigation participant administered a pharmaceutical product and that does not necessarily have to have a causal relationship with this treatment.

An AE can therefore be:

- Any unfavorable and unintended sign (including an abnormal laboratory finding), symptom, or disease temporally associated with the use of a medicinal product, whether or not considered related to the medicinal product.

Events Meeting the AE Definition:

- Deterioration in a laboratory value (hematology, clinical chemistry, or urinalysis) or other clinical test (e.g., ECG, x-ray) that is associated with symptoms or leads to a change in study treatment or concomitant treatment or discontinuation from study treatment (see [Appendix 3, Section 4](#)).
- Exacerbation of a chronic or intermittent preexisting condition, including either an increase in frequency and/or intensity of the condition.
- New conditions detected or diagnosed after study treatment administration even though it may have been present before the start of the study.
- AEs that are related to a protocol-mandated intervention, including those that occur prior to assignment of study treatment (e.g., screening invasive procedures such as biopsies).

Events NOT Meeting the AE Definition:

- Any clinically significant abnormal laboratory findings or other abnormal safety assessments that are associated with the underlying disease, unless judged by the Investigator to be more severe than expected for the participant's condition.
- The disease/disorder being studied or expected progression, signs, or symptoms of the disease/disorder being studied, unless more severe than expected for the participant's condition.
- Medical or surgical procedure (e.g., endoscopy, appendectomy): The condition that leads to the procedure is an AE.
- Situations where an untoward medical occurrence did not occur (social and/or convenience admission to a hospital).
- Anticipated day-to-day fluctuations of preexisting disease(s) or condition(s) present or detected at the start of the study that do not worsen.

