2. DEFINITION OF SERIOUS ADVERSE EVENTS

If an event is not an AE per definition above, then it cannot be an SAE even if serious conditions are met (e.g., hospitalization for signs/symptoms of the disease under study, death due to progression of disease).

An SAE is defined as any untoward medical occurrence that at any dose:

- **Results in death.**
- **Is life-threatening.**

The term "life-threatening" in the definition of "serious" refers to an event during which the participant was at risk of death at the time of the event; it does not refer to an event which hypothetically might have caused death if it was more severe.

- **Requires inpatient hospitalization or prolongation of existing hospitalization** (see [Appendix 3](#)).

In general, hospitalization signifies that the participant has been detained (usually involving at least an overnight stay) at the hospital or emergency ward for observation and/or treatment that would not have been appropriate in the physician's office or outpatient setting. Complications that occur during hospitalization are AEs. If a complication prolongs hospitalization or fulfills any other serious criteria, the event is serious. When in doubt as to whether "hospitalization" occurred or was necessary, the AE should be considered serious.

- **Results in persistent or significant disability/incapacity**

Disability means substantial disruption of the participant's ability to conduct normal life functions.

This definition is not intended to include experiences of relatively minor medical significance such as uncomplicated headache, nausea, vomiting, diarrhea, influenza, and accidental trauma (e.g., sprained ankle) which may interfere with or prevent everyday life functions but do not constitute a substantial disruption.

- **Is a congenital anomaly/birth defect.**

- **Other significant events:**

Medical or scientific judgment should be exercised in deciding whether SAE reporting is appropriate in other situations such as important medical events that may not be immediately life-threatening or result in death or hospitalization but may jeopardize the participant or may require medical or surgical intervention to prevent one of the other outcomes listed in the above definition. These events should usually be considered serious.

Examples of such events include

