6 CONGENITAL ANOMALIES/BIRTH DEFECTS

Any congenital anomaly/birth defect in a child born to a participant or partner of a male participant exposed to study treatment should be classified as an SAE, recorded on the Adverse Event eCRF, and reported to the Sponsor immediately (i.e., no more than 24 hours after learning of the event).

Appendix 6

Investigational Medicinal Product and Non-Investigational Medicinal Product Designations

Table 1 *Investigational, Authorized Auxiliary, and Unauthorized Auxiliary Medicinal Product Designations for European Economic Area*

| Product Name | IMP/AxMP Designation | Marketing Authorization Status in EEA | Used within Marketing Authorization |
|-------------------|---|---------------------------------------|-------------------------------------|
| RO7565020 | IMP (test product) | Unauthorized | Not applicable |
| RO7565020 placebo | IMP (placebo) | Unauthorized | Not applicable |
| ETV | Authorized AxMP (background treatment) | Authorized | Yes |
| TDF | Authorized AxMP (background treatment) | Authorized | Yes |
| TAF | Authorized AxMP (background treatment) | Authorized | Yes |

Abbreviations: AxMP = auxiliary medicinal product; EEA = European Economic Area; ETV = entecavir; IMP = investigational medicinal product; TAF = tenofovir alafenamide; TDF = tenofovir disoproxil fumarate.

Table 2 *Investigational and Non-Investigational Medicinal Product Designations for the United Kingdom*

| Product Name | IMP/NIMP Designation | Marketing Authorization Status in the UK | Used within Marketing Authorization |
|-------------------|------------------------------------|--|-------------------------------------|
| RO7565020 | IMP (test product) | Unauthorized | Not applicable |
| RO7565020 placebo | IMP (placebo) | Unauthorized | Not applicable |
| ETV | NIMP (background treatment) | Authorized | Yes |
| TDF | NIMP (background treatment) | Authorized | Yes |
| TAF | NIMP (background treatment) | Authorized | Yes |

Abbreviations: ETV = entecavir; IMP = investigational medicinal product; NIMP = non-investigational medicinal product; TAF = tenofovir alafenamide; TDF = tenofovir disoproxil fumarate, UK = United Kingdom.

Appendix 7

Abbreviations

| Abbreviation | Definition |
|----------------------------|--|
| AAV | adeno-associated virus |
| Ab | antibody |
| ADA | anti-drug antibody |

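### Miscarriages in male participants' partners, and anomalies in their children, are recorded as SAEs on the Adverse Event eCRF, and no rule keeps them out of the SAE frequency of dosed participants

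*Combined protocol and SAP*

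**What the plan says.** **Recording rule.** Appendix 5, Section 5 covers a spontaneous abortion in a participant or in "the partner of a male participant exposed to study treatment should be classified as an SAE". The event is to be "recorded on the Adverse Event eCRF, and reported to the Sponsor immediately". Appendix 5, Section 6 gives infant outcomes the same SAE status and the same eCRF entry: "Any congenital anomaly/birth defect in a child born to a participant or partner of a male participant exposed to study treatment should be classified". Section 8.3.5 agrees: after covering male participants' partners, it treats abnormal pregnancy outcomes as SAEs.

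**Definition.** Appendix 2, Section 1 defines an AE as "any untoward medical occurrence in a participant or clinical investigation participant administered a pharmaceutical product". Appendix 2, Section 2 adds: "If an event is not an AE per definition above, then it cannot be an SAE even if serious conditions are met".

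**Analysis.** The primary endpoint in Section 3 is the frequency and severity of AEs, including SAEs. Under Section 9.4.2, Table 11, the Sponsor codes the terms that the Investigator enters on the eCRF, and "Frequency and severity of adverse events will be summarized". Section 9.3 limits the safety analysis set to participants who received at least one dose. Nothing in these sections flags, excludes or separately tabulates a partner or infant event.

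**Whose partners.** Appendix 5, Section 4 restricts the collection of partner pregnancies to men who receive RO7565020. Sections 5.1.1 and 5.2.1 require no contraception of male participants.

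**The concern.** Appendix 5 makes a partner's miscarriage an SAE. On a plain reading of Appendix 2 it cannot be one, because the partner is not a participant and was not given the product. Both instructions cannot be followed to the letter.

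The conflict matters because of what follows in the analysis. The safety set decides who is in the denominator. It does not decide which eCRF entries reach the numerator. If a partner event is on the Adverse Event eCRF and the summaries are built from that form, the default result is that a dosed man who had no event is counted with an SAE. In Part 1 this could happen only among men on RO7565020, so the comparison with pooled placebo would tilt against the active drug for a reason unrelated to tolerability. If the question is settled only after an event occurs, Sponsor staff who are unblinded under Section 6.3.2 would be making an ad hoc choice.

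**Working it through.** **1. The plan's own figures.** Section 9.2 gives at least an 80% chance of seeing one or more AEs with 5 participants at 28% incidence, and with 6 participants at 24%. From 1 − (1 − p)^n:

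- n = 5, p = 0.28: 1 − 0.72^5 = 0.8065
- n = 6, p = 0.24: 1 − 0.76^6 = 0.8073

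Both reproduce. The present point does not depend on them, but they show that the plan reads cohorts at the level of a single event.

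**2. Effect of one entry.** Exact (Clopper-Pearson) 95% intervals, given for scale; the plan does not list them as outputs.

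| Group | No entry | One partner entry |
|---|---|---|
| Cohort, 6 active | 0/6 = 0% (0 to 45.9%) | 1/6 = 16.7% (0.4 to 64.1%) |
| Dose review, 5 active | 0/5 = 0% (0 to 52.2%) | 1/5 = 20% (0.5 to 71.6%) |
| Part 1, 42 active | 0/42 = 0% (0 to 8.4%) | 1/42 = 2.4% (0.06 to 12.6%) |

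**3. How often.** Part 1 has up to 7 cohorts of 6 active participants, so at most 7 × 6 = 42 active men. The documents give no conception or pregnancy-loss rates. Assume 2 to 8% of men have a partner who conceives during the period, and 10 to 20% of those pregnancies are lost.

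- Per active man: 0.02 × 0.10 = 0.002 to 0.08 × 0.20 = 0.016 expected events.
- Cohort of 6 men: 6 × 0.002 = 0.012 to 6 × 0.016 = 0.096. From 1 − exp(−e), the chance of at least one event is 1.2% to 9.2%.
- Part 1, upper end: 42 × 0.016 = 0.67, a chance of about 49%.
- Part 1, lower end, assuming 25 active men: 25 × 0.002 = 0.05, a chance of about 5%.

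Parts 2 and 3 (30 to 54 participants, all on active drug) are outside these Part 1 totals. They would add in proportion to the men enrolled.

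**4. Which events fall inside the AE window.** Section 8.3.1 collects AEs until the last scheduled follow-up visit, which in Part 1a is 36 weeks after the dose. A miscarriage can fall within that time. A term birth conceived after dosing would ordinarily fall later, and under Appendix 2, Section 5.1 it would then be reported as a post-study event only if believed related. The multiple-dose parts and the extended follow-up in Parts 2 and 3 leave more room for births, but the miscarriage rule is the one that matters most in practice.

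**The case against.** **A deliberate, specific rule.** Sections 5 and 6 of Appendix 5 and Section 8.3.5 agree with one another. Appendix 2, Section 2 itself lists congenital anomaly as a seriousness criterion. Its sentence barring non-AEs from being SAEs is illustrated by hospitalisation for, and death from, the disease under study, so pregnancy outcomes may not have been in mind. A specific rule may extend a general definition. This stands as an explanation of the drafting, and it supports keeping the expedited reporting. It does not settle the tabulation, because a reporting rule does not say what belongs in a participant-level frequency.

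**Counting is an inference.** No passage states that partner events are counted, and the eCRF layout is not in the documents. Section 9.4.2 summarises participants by cohort, and AEs are also listed, so a miscarriage recorded under a man would be recognisable. All of that is correct. The claim is about the default when the written rules are applied, not about a stated intention.

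**Stopping rules.** A reader might infer that a partner event judged related would trigger the rule "Any serious adverse reaction in 1 participant (i.e., a serious AE [SAE] considered to be related to RO7565020" in Section 4.1.1.3.1. The documents do not support that reading. The Part 1 lead-in limits the rule to what occurs in participants treated with RO7565020, the Parts 2 and 3 item also refers to a participant, and Section 4.1.1.3.2 concerns what the participant experiences.

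**Size.** A reader might count all 56 Part 1 enrolees as men at risk, giving 56 × 0.08 × 0.20 = 0.90 expected events (59%). That includes placebo recipients, whose partners' pregnancies Appendix 5, Section 4 does not collect.

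**Removing the events from the eCRF.** A reader might conclude that they should leave the Adverse Event eCRF altogether. Under Appendix 2, Section 5.1 the EDC entry generates the report to the Sponsor's safety department, so that would remove a working safety route.

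**Conclusion.** The point holds as a conflict between a recording rule and the plan's own AE definition, together with a missing analysis convention. By default, a miscarriage in the partner of a man on RO7565020, and less often an anomaly in the child, would enter the SAE frequency of dosed participants. One entry takes a cohort from 0/6 to 1/6.

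The practical size is modest. The analysis is descriptive, with no hypothesis tests. The upper expectation of 0.67 events in Part 1 requires every active participant to be male and both assumed rates to be at their maximum. The active-only tilt rests on the collection limit in Appendix 5, Section 4. Sections 5 and 6 refer to study treatment, which under Section 6 of the protocol includes placebo. The definitional conflict does not depend on the assumed rates. The point does not extend to a claim that the stopping rules would be triggered.

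**What to change.** 1. Keep the existing 24-hour EDC and eCRF reporting for partner and infant outcomes, and add a flag that identifies the affected person as a partner or infant.
2. In Section 9.4.2, state that flagged events are listed separately and excluded from participant-level AE and SAE frequencies.
3. Reconcile Appendix 5, Sections 5 and 6 (and Section 8.3.5) with Appendix 2, Sections 1 and 2, for example by saying that these outcomes are reported as SAEs for safety purposes but are not AEs of the participant.
4. Check that the reconciled text is consistent with Section 4.1.1.3, which is already worded for events in participants. This review proposes no change to the stopping rules.

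The cost is wording in Appendices 2 and 5, one sentence in Section 9.4.2, one extra eCRF flag and one extra listing. No safety information is lost.

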6 CONGENITAL ANOMALIES/BIRTH DEFECTS

Any congenital anomaly/birth defect in a child born to a participant or partner of a male participant exposed to study treatment should be classified as an SAE, recorded on the Adverse Event eCRF, and reported to the Sponsor immediately (i.e., no more than 24 hours after learning of the event).

Appendix 6

Investigational Medicinal Product and Non-Investigational Medicinal Product Designations

Table 1 *Investigational, Authorized Auxiliary, and Unauthorized Auxiliary Medicinal Product Designations for European Economic Area*

| Product Name | IMP/AxMP Designation | Marketing Authorization Status in EEA | Used within Marketing Authorization |
|-------------------|---|---------------------------------------|-------------------------------------|
| RO7565020 | IMP (test product) | Unauthorized | Not applicable |
| RO7565020 placebo | IMP (placebo) | Unauthorized | Not applicable |
| ETV | Authorized AxMP (background treatment) | Authorized | Yes |
| TDF | Authorized AxMP (background treatment) | Authorized | Yes |
| TAF | Authorized AxMP (background treatment) | Authorized | Yes |

Abbreviations: AxMP = auxiliary medicinal product; EEA = European Economic Area; ETV = entecavir; IMP = investigational medicinal product; TAF = tenofovir alafenamide; TDF = tenofovir disoproxil fumarate.

Table 2 *Investigational and Non-Investigational Medicinal Product Designations for the United Kingdom*

| Product Name | IMP/NIMP Designation | Marketing Authorization Status in the UK | Used within Marketing Authorization |
|-------------------|------------------------------------|--|-------------------------------------|
| RO7565020 | IMP (test product) | Unauthorized | Not applicable |
| RO7565020 placebo | IMP (placebo) | Unauthorized | Not applicable |
| ETV | NIMP (background treatment) | Authorized | Yes |
| TDF | NIMP (background treatment) | Authorized | Yes |
| TAF | NIMP (background treatment) | Authorized | Yes |

Abbreviations: ETV = entecavir; IMP = investigational medicinal product; NIMP = non-investigational medicinal product; TAF = tenofovir alafenamide; TDF = tenofovir disoproxil fumarate, UK = United Kingdom.

Appendix 7

Abbreviations

| Abbreviation | Definition |
|----------------------------|--|
| AAV | adeno-associated virus |
| Ab | antibody |
| ADA | anti-drug antibody |
| ADCP | antibody-dependent cellular phagocytosis |
| AE | adverse event |
| AESI | adverse event of special interest |
| AFP | α -fetoprotein |
| ALT | alanine aminotransferase |
| AMA | antimitochondrial antibody |
| ANA | antinuclear antibody |
| ARFI | acoustic radiation force impulse |
| ASMA | anti-smooth muscle antibody |
| AST | aspartate aminotransferase |
| a-TPO | anti-thyroperoxidase |
| AUC_{0-21d} | area under the time-concentration curve from 0 to 21 days |
| AUC_{inf} | area under the time-concentration curve from 0 to infinity |
| AUC_{last} | area under the time-concentration curve from 0 to last sampling point or last quantifiable sample, whichever comes first |
| AUC_{tau} | area under the time-concentration curve within a dosing interval |
| AxMP | auxiliary medicinal product |
| BMI | body mass index |
| cccDNA | covalently closed circular DNA |
| CHB | chronic hepatitis B |
| CL | clearance |
| CL/F | apparent clearance |
| C_{max} | maximum concentration |
| COVID-19 | coronavirus disease 2019 |
| CSR | clinical study report |
| DAIDS | Division of AIDS |
| DBP | diastolic blood pressure |
| DDT | Dose Decision Team |
| DEP | Dose Escalation Plan |

| | |
|---------------|---|
| DNA | deoxyribonucleic acid |
| EASL | European Association for the Study of the Liver |
| ECG | electrocardiogram |
| eCRF | electronic case report form |
| eTMF | electronic trial master file |
| ETV | entecavir |
| E.U. | European Union |
| FcRn | neonatal Fc receptor |
| FIH | First-in-human |
| HAV | hepatitis A virus |
| HBcAg | hepatitis B core antigen |
| HBcrAg | hepatitis B core-related antigen |
| HBeAg | hepatitis B e antigen |
| HBsAb | hepatitis B surface antibody |
| HBsAg | hepatitis B surface antigen |
| HBV | hepatitis B virus |
| HCC | hepatocellular carcinoma |
| HCV | hepatitis C virus |
| HDV | hepatitis D virus |
| HEV | hepatitis E virus |
| HIV | human immunodeficiency virus |
| HLA | human leukocyte antigen |
| HSV | herpes simplex virus |
| IA | interim analysis |
| ICF | Informed Consent Form |
| ICH | International Council for Harmonisation |
| IEC | Independent Ethics Committee |
| IFN | interferon |
| IgG | immunoglobulin G |
| IgM | immunoglobulin M |
| IL | interleukin |
| IMP | investigational medicinal product |
| INR | international normalized ratio |
| IRB | Institutional Review Board |
| IRR | infusion-/injection-related reaction |
| IV | intravenous |
| IxRS | interactive (voice/web) response system |
